Document Type:
Study Protocol with Statistical Analysis Plan (SAP)

Official Title of Study:
**Effects of Personalized Actionable Connected Extensible (PACE) Interventions
Among Patients With Chronic Kidney Disease**

NCT Number:
NCT06065501

Document Date:
05/20/2025

Subtitle:
Main Protocol – Taiwan Implementation Site

Sponsor:
National Cheng Kung University Hospital

Principal Investigator:
[name](c), RN

- Study Objectives: To examine the effectiveness Personalized Actionable Connected Extensible (PACE) Interventions for frailty among patients with CKD.
- Study Design: A randomized controlled trial with a single-blinded experimental design.
- Eligibility Criteria:
 1. The eligibility criteria included: (1) age 20 years or older; (2) diagnosis of CKD stage 1 to 5 for at least 6 months; (3) identified as frail; (4) the ability to communicate in Mandarin Chinese or Taiwanese; and (5) willingness to participate in the study.
 2. The exclusion criteria were: (1) receiving renal replacement therapy, (2) a history of mental illness, and (3) having reached TTM stage 5.
- Intervention/Comparator Descriptions:
 1. The PACE intervention involves using Line (technological devices) to establish a collaborative group with patients. The researchers will regularly provide reminders to chronic kidney disease patients regarding the importance of nutrition and exercise. They will also provide information on how to adhere to nutritional and exercise regimens, offering praise for consistent performance.
 2. Nurses provide routine education and consultation.
- Outcome Measures:
 1. Primary Outcome Measure: Tilburg Frailty Indicator (TFI)
 2. Secondary Outcome Measures: International Physical Activity Questionnaires (IPAQ, Taiwan Version); Health-promoting Lifestyle Behaviors (HPLP-II, Taiwan Version); Mini Nutritional Assessment Short-Form (MNA-SF, Taiwan Version)
- Statistical Analysis Plan:
 1. Descriptive Statistics: Mean \pm SD for continuous variables, Frequency (%) for categorical variables

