 2. Comparative Analysis: Generalized estimating equations (GEE) are used to account for the non-independence of repeated measures over time within individuals and to control for potential confounding factors. The GEE models included main effects for group (intervention vs. control), time, and group-by-time interaction terms to examine whether there were statistically significant differences in outcome trajectories between the two groups over time. Covariates controlled in the models included age and gender. A significance level of 0.05 was used for hypothesis testing. All analyses were conducted using SPSS 25 version software.

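### The TFI model does not adjust for baseline TFI, which gives up precision; one deciding test should be named when this is corrected

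*Combined protocol and SAP*

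**What the plan says.** Outcome Measures, item 1, names the TFI as the primary outcome and attaches no assessment time or summary measure to it.

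The whole inferential plan is in the Statistical Analysis Plan, item 2 (Comparative Analysis). On the model: "The GEE models included main effects for group (intervention vs. control), time, and group-by-time interaction terms". The stated purpose is "to examine whether there were statistically significant differences in outcome trajectories between the two groups over time". On adjustment: "Covariates controlled in the models included age and gender". On error: "A significance level of 0.05 was used for hypothesis testing".

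The documents do not say:
- how many follow-up visits there are, or when;
- whether time is categorical or linear;
- whether baseline TFI is a response in the model;
- which coefficient or joint test decides the primary result.

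No sample size, power, effect size or correlation is given either. Eligibility Criteria, item 1, requires patients to be "identified as frail" at entry, without naming the instrument.

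**The concern.** A baseline measurement of the outcome is usually one of the strongest predictors of the follow-up value, and it is absent from the named covariates. Because the model is for repeated measures and relies on the group-by-time interaction, the natural reading is that baseline TFI enters as the first response. The interaction then compares change from baseline between arms. That comparison is valid, but it subtracts the whole baseline value even when follow-up tracks baseline only in part, and so carries avoidable noise. At stake is power on the primary outcome for the same patients.

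A second, smaller matter is that the plan names no single test. If there is more than one follow-up, a reader could not tell from the plan which result was meant to decide.

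**Working it through.** **Inputs.** From the documents: TFI as primary outcome; a GEE with group, time and interaction; age and gender as covariates; level 0.05. Assumed, because the documents give no figure: the same variance at every visit, the same correlation rho between any two visits (given age and gender), rho from 0.5 to 0.8, 1 to 4 follow-ups, and large samples. All results below are illustrative.

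**The plan's own figure.** One pre-named test at 0.05 has a type I error of 0.050. There is no sample size or power statement to reproduce.

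**Precision of the two analyses.** Let σ² be the variance of TFI at a visit. Per patient:
- change from baseline: variance 2σ²(1 − rho);
- follow-up adjusted for baseline: variance σ²(1 − rho²).

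The arm sizes enter both in the same way and cancel. The ratio is (1 − rho²) / [2(1 − rho)] = (1 + rho)/2.

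| rho | variance ratio | equivalent gain in patients |
|---|---|---|
| 0.5 | 0.75 | 1/0.75 = 1.33 times |
| 0.8 | 0.90 | 1/0.90 = 1.11 times |

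**Power.** Set the effect so that the change contrast has 80% power. Its mean z is then 1.960 + 0.842 = 2.802. With adjustment the mean z is 2.802/√ratio:
- rho 0.5: 2.802/√0.75 = 3.235, power Φ(3.235 − 1.960) = 0.899;
- rho 0.8: 2.802/√0.90 = 2.953, power Φ(2.953 − 1.960) = 0.840.

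**Why the test must change with the model.** Once baseline is a covariate and only follow-up visits are responses, the interaction measures only whether the group difference varies among follow-ups. A benefit that is the same at every follow-up contributes nothing to it. For 2, 3 or 4 follow-ups the power of the interaction test against such a benefit is 0.050, no more than its error rate. The group difference itself has to be tested.

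**Which group difference, if there are several follow-ups.** Two choices each hold 5%. Adjusted power, over 2 to 4 follow-ups:

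| Pattern of effect | rho | joint test of all follow-up differences | difference at the final visit |
|---|---|---|---|
| Sustained | 0.5 | 95–97% | 90% |
| Sustained | 0.8 | about 89% | 84% |
| Growing linearly | 0.5 | about 84% | 90% |
| Growing linearly | 0.8 | 74–76% | 84% |

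Neither is better throughout.

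**Type I error under the plan as written.** With one follow-up, with linear time, or with one joint test, the error is 0.050. A null simulation with baseline as a response gave 0.050, within simulation error, for the joint and linear-time tests at 1 to 4 follow-ups. Only if any significant visit-specific term were allowed to count would it rise, as follows:

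| Visit terms | correlation 0.9 between terms | correlation 0.5 between terms |
|---|---|---|
| 2 | 7.0% | 9.1% |
| 3 | 8.4% | 12.5% |
| 4 | 9.4% | 15.6% |

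The value 0.5 is the one that follows from equal correlation between all visits with a shared baseline.

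**The case against.** The strongest defence is that the planned analysis is valid as it stands. With baseline as a response, the interaction already takes account of baseline, and adjustment is an optional gain whose size rests on correlations the documents do not give. The SAP also says that the covariates included age and gender, which need not be a complete list. All of this stands, and it limits the point to efficiency. It does not remove the point: under the stated assumptions the adjusted analysis is more precise for any rho below 1, and if baseline TFI was meant to be a covariate the plan should say so.

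A reader might infer something stronger: that the 5% level is breached, or that the short covariate list contributes to a breach. The documents do not support either. In a randomized comparison a fixed covariate list does not inflate type I error. The interaction terms are given one purpose, "to examine whether there were statistically significant differences in outcome trajectories between the two groups over time", and that fits a single overall group-by-time test, which holds 5%. The rule that any visit may count is not written anywhere, and the number of visits and their correlation are unknown. The 7–16% figures for two to four visits show what such a rule would do; they do not measure a defect in this plan.

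It might also be inferred that the trial must adopt a final-visit contrast or categorical time. Those are choices. A pre-specified joint test is equally valid and lies closer to the trajectory aim.

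**Conclusion.** The concern holds as a loss of precision on the primary outcome. If baseline TFI is a response, adding it as a covariate instead would cut the variance of the treatment contrast by 10% to 25%, worth about 4 to 10 percentage points of power from a starting point of 80%. This rests on equal variances and an exchangeable correlation of 0.8 to 0.5, neither of which comes from the documents, and on TFI being measured at baseline, which the repeated-measures model implies but does not state.

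The missing visits, time coding and deciding test are mainly missing detail. With a single follow-up they make no difference to type I error. With two or more, naming one test closes the gap. The plan's text does not show that error exceeds 5%.

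**What to change.** In the primary TFI model, add baseline TFI as a covariate alongside age and gender, and use only follow-up TFI values as responses. State the visits and the coding of time. Define the treatment effect as the group difference at follow-up:
- with one follow-up, the group term;
- with more than one, a single pre-named two-sided 0.05 test: either a joint test of the group differences at all follow-ups, or the difference at one named visit.

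Do not let the interaction alone decide, since in this model it would miss a sustained benefit. Report the remaining terms and visits as supportive.

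The cost is SAP wording and one covariate, with no new data if TFI was measured at baseline. Patients with no follow-up TFI drop out of the primary model, so their number should be reported by arm. A joint test has no direction; a single-visit contrast ignores differences confined to other visits.

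The analysis section is written in the past tense ("All analyses were conducted using SPSS 25 version software"), so analysis may already have been done. If it has, these choices should be labelled post hoc and reported beside the analysis actually run.
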